5.0 Study Design

Specific Aim 1: This is a randomized, double-blind, placebo-controlled, cross-over experimental design. Participants will be asked to complete 5 visits to the laboratory; one informed consent/screening visit and 4 study visits. During the informed consent/screening visit, participants will complete the informed consent, eligibility criteria will be presented, resting blood pressure and heart rate (derived from the blood pressure measurement) will be measured, and participants will complete the following questionnaires: iPAQ, PAR-Q, and Health

History Questionnaire. During the study visits, participants will undergo baseline measurements (described in detail in Section 7.0) followed by ingesting either a placebo or 3 different doses of mirabegron (100 mg, 150 mg, or 200 mg). Mirabegron will be prescribed by our study physician, [name]. [name] is a physician in the Department of Emergency Medicine at Indiana University Health and he is a Fellow in Wilderness Medicine through the Wilderness Medical Society as well as a member of the Indiana Task Force 1 (part of the FEMA Urban Search and Rescue System. [name] will determine if it is safe for a potential participant to stop their medication for 5 half-lives during screening. [name] will also review health history, resting heart rate and blood pressure measurements, and contraindications for mirabegron use to determine eligibility. A second set of baseline measurements will be made prior to participants entering our whole-body indirect calorimeter set at 20°C (68°F) for 6 hours. Every 30 minutes in the chamber, participants will be asked to assume the supine position to record resting energy expenditure (i.e., thermogenesis) and other physiological variables (described in detail in Section 7.0). This design will allow us to determine which dose of mirabegron produces the greatest increase in thermogenesis.

Informed Consent/Screening Visit: Obtain informed consent. Screen potential participants by inclusion and exclusion criteria. Obtain Health History Questionnaire, PAR-Q+, and IPAQ and resting heart rate and blood pressure. Perform body composition assessment with DEXA.

Study Visits 1-4

The order of placebo and mirabegron doses (100 mg, 150 mg, and 200 mg) will be randomized among Study Visits 1-4. All study procedures will be identical between Study Visits.

For specific study protocol and data collection procedures, please see Sections 7.0 and 8.0.

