Specific Aim 2: This is a randomized, double-blind, placebo-controlled, cross-over experimental design. Participants will be asked to complete 3 visits to the laboratory; one informed consent/screening visit and 2 study visits. During the informed consent/screening visit, participants will complete the informed consent, eligibility criteria will be presented, resting blood pressure and heart rate (derived from the blood pressure measurement) will be measured, and participants will complete the following questionnaires: IPAQ, PAR-Q, and Health History Questionnaire. During the study visits, participants will undergo baseline measurements (described in detail in Section 7.0) followed by ingesting either a placebo or one dose of mirabegron (100 mg) prior to entering our water immersion tank. Mirabegron will be prescribed by our study physician, [name] (Department of Emergency Medicine, Indiana University Health). The dose of mirabegron that will be used for Specific Aim 2 is dependent on our findings from Specific Aim 1. The dose of mirabegron that elicits the greatest increase in thermogenesis in Specific Aim 1 will be used for Specific Aim 2. A second set of baseline measurements will be made and then the water immersion tank will then be rapidly filled with 35°C (95°F) water. The temperature of the water will be progressively lowered by ~12°C every 60 minutes until the water temperature reaches 10°C (50°F) or until the participant can no longer tolerate the cold or if rectal temperature reaches 35.5°C (95.9°F). Participants will be continuously monitored for rectal temperature, indices of shivering, skin temperature, heart

rate, blood pressure, and thermal perceptions (described in detail in Section 7.0). This design will allow us to determine if mirabegron improves cold water immersion tolerance.

Informed Consent/Screening Visit: Obtain informed consent. Screen potential participants by inclusion and exclusion criteria. Obtain Health History Questionnaire, PAR-Q+, and IPAQ and resting heart rate and blood pressure. Perform body composition assessment with DEXA.

Study Visits 1-2
 The order of placebo and mirabegron (100 mg) will be randomized between Study Visits 1-2. All study procedures will be identical between Study Visits. For specific study protocol and data collection procedures, please see Sections 7.0 and 8.0

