6.0 Enrollment/Randomization

We plan to recruit 60 total participants for this project (30 for Specific Aim 1 and 30 for Specific Aim 2). Participants who partake in Specific Aim 1 will also be used for Specific Aim 3 and can participate in Specific Aim 2. Two informed consent forms will be used for Specific Aim 1 & 3 (Mirabegron and Thermogenesis in Cold Air) and Specific Aim 2 (Mirabegron and Thermogenesis in Cold Water).

Participants will be recruited from the IU student body and local citizen population through flyers placed around campus, announcements made to classes of students, and word of mouth. Participants who are interested will contact the principal investigator or IRB approved personnel by email or by phone. This population may include IU students and individuals outside the IU community.

Potential participants will be given the basic information about the study and schedule an appointment for screening if they indicate that they would be interested in participating. Participants will be provided with detailed description of study procedures prior to study enrollment. Participants will be asked to read the consent form at this time and encouraged to ask any questions. Participants can then: 1) sign the consent form; 2) take it home for further consideration; or 3) decide not to participate. Participants will be screened once written informed consent has been given.

Both Specific Aim 1 (& 3) and Specific Aim 2 study visits will be completed in a randomized order. Randomization of the order of the study visits will be completed by a research technician using a

randomization list that will be created by a trained statistician external to the research team using R (R Foundation for Statistical Computing, Vienna, Austria) and our subjects will be randomized by our research technician.

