11.0 Study Withdrawal/Discontinuation

Participants can voluntarily withdraw from the study at any time by contacting any of the researchers on the study via any available means (personal contact, email, phone, etc.). If a researcher on the project wishes to withdraw a participant from the study, they will contact the participant directly (personal contact, phone, email, etc.). Possible indications for withdrawal by a researcher include a change in their health history that excludes them from participation and an inability to keep appointments or follow or understand the rules of the protocol. Data collected up to the time of withdraw (either voluntary or by the study team) may be used for analysis.

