12.0 Statistical Considerations

Specific Aim 1

Power Analysis: Using data from Loh et al. (2) we expect to observe an effect size (δ) of 0.90 for the comparison of resting energy expenditure in the placebo condition versus 200 mg of mirabegron. Given this effect size, 10 participants will be needed to achieve a power of 0.99 with an alpha level set at 0.05. To account for possible attrition, we plan on recruiting up to 30 participants.

Statistical Approach: We will compare the primary (i.e., thermogenesis) and secondary (i.e., core temperature, skin temperature, heart rate, blood pressure, indices of shivering, thermal perceptions, and infrared thermography images) dependent variables using mixed effects ANOVA (i.e., mirabegron dose x time) followed by Tukey's post hoc procedure if a significant interaction or main effect is found from the ANOVA analyses. We will also calculate the thermogenesis area under the curve for each dose of mirabegron. These values will be compared using repeated measures ANOVA followed by Tukey's post hoc procedure if a significant main effect is found from the ANOVA analysis. We will also perform correlation analyses to determine the relation between body composition and our primary and secondary dependent variables. The alpha level will be set at $P < 0.05$ for all analyses.

Specific Aim 2

Power Analysis: Similar to Specific Aim 1 and the data from Loh et al. (2), we expect to observe an effect size (δ) of 0.90 for the comparison of rectal temperature in the placebo condition versus the mirabegron condition. Given this effect size, 10 participants will be needed to achieve a power of 0.99 with an alpha level set at 0.05. To account for possible attrition, we plan on recruiting up to 30 participants.

Statistical Approach: The primary (i.e., core temperature deflection point) and secondary (i.e., onset of shivering inflection point) dependent variables from the mirabegron and placebo trials will be compared using paired t-tests to determine if mirabegron improves cold-water immersion tolerance. Mixed effects ANOVA will be used to compare the remaining dependent variables between conditions (i.e., mirabegron vs. placebo) and across time. If a significant

interaction or main effect results from the ANOVA analyses, we will use the Holm-Sidak post hoc test to determine where differences exist. The alpha level will be set at $P < 0.05$ for all analyses.

Specific Aim 3

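### Fitted classically, the Aim 1 thermogenesis AUC analysis keeps only four-visit completers, and neither crossover model includes visit: a modest, conditional loss of precision that is cheap to avoid

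*Combined protocol and SAP*

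**What the plan says.** All references are to the combined protocol and SAP.

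- **Aim 1 models (section 12.0).** Thermogenesis and the secondary measures are compared as "dependent variables using mixed effects ANOVA (i.e., mirabegron dose x time) followed by" Tukey's procedure. The AUC has its own analysis: "These values will be compared using repeated measures ANOVA followed by" Tukey's procedure. Section 3.1 lists this AUC among the Aim 1 primary outcomes.
- **Aim 2 models (section 12.0).** The core temperature deflection point and the shivering inflection point are "compared using paired t-tests to determine if mirabegron improves cold-water immersion tolerance". The other variables go into a mixed effects ANOVA by condition and time.
- **Order (section 5.0).** For Aim 1: "The order of placebo and mirabegron doses (100 mg, 150 mg, and 200 mg) will be randomized among Study Visits 1-4". For Aim 2: "The order of placebo and mirabegron (100 mg) will be randomized between Study Visits 1-2". Section 6.0 says the order comes from a "randomization list that will be created by a trained statistician external to the research team using R". Neither section says whether the sequences are balanced.
- **Partial data (section 11.0).** "Data collected up to the time of withdraw (either voluntary or by the study team) may be used for analysis". No method is given. Section 12.0 expects some attrition and recruits up to 30 per aim, but gives no rate.
- **Sample size (section 12.0).** An effect size of 0.90 is assumed, and "Given this effect size, 10 participants will be needed to achieve a power of 0.99 with an alpha level set at 0.05". The plan does not say whether 0.90 is standardized by the SD of the paired difference or by the between-person SD.

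**The concern.** Two features could waste information.

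The first is lost visits. A classical repeated measures ANOVA needs a complete row per participant, so anyone who misses one of the four Aim 1 conditions drops out of the AUC comparison. Section 7.0 sets gaps of at least 10 days with a goal of 10 to 14, so four visits span about 30 to 42 days and some loss is plausible. This point concerns the Aim 1 AUC only. The dose x time mixed model can already keep partial participants, and in Aim 2 a participant with one visit adds almost nothing to a within-person contrast.

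The second is visit. If responses differ between visits, for example through habituation, a model without visit leaves that difference in the error. With unequal sequence counts, a chance split also moves the estimate in this particular trial. What is at stake is precision.

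**Working it through.** **1. The plan's own figure.** Paired t-test, n = 10, two-sided 0.05, noncentrality = effect x sqrt(10):
- paired effect 0.90 gives power 0.717;
- paired effect 1.54 gives power 0.990.

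A between-condition effect of 0.90 gives a paired effect of 0.90 / sqrt(2(1 - r)), which is about 1.54 when the within-person correlation r is about 0.83. Both values are carried below because the plan does not define 0.90.

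**2. Assumptions not in the documents.** Loss before each later visit is 5% or 10%. The visit shift is expressed in SDs of the paired difference (0, 0.25, 0.5). In Aim 1 the four conditions have means 0, 0.45, 0.675 and 0.9 in the same units, and the visit trend is linear from visit 1 to visit 4.

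**3. Aim 1 AUC, lost visits.** Expected completers of 30: at 5% loss, 30 x 0.95^3 = 25.7; at 10% loss, 30 x 0.90^3 = 21.9. The ratio of SEs for 200 mg versus placebo (all visits with a visit term and balanced orders, over completers only; within-person correlation 0.5 to 0.8) is:

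| Loss before each later visit | SE ratio |
|---|---|
| 0% | 1.00 |
| 5% | 0.97 |
| 10% | 0.94 |
| 20% | 0.86 to 0.88 |

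Simulated power for 200 mg versus placebo (significant F, then Tukey; Williams orders; 10% loss):

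| Shift | Completers, no visit | Completers, visit | All visits, no visit | All visits, visit |
|---|---|---|---|---|
| 0 | 0.929 | 0.927 | 0.959 | 0.955 |
| 0.25 | 0.918 | 0.917 | 0.952 | 0.953 |
| 0.5 | 0.908 | 0.925 | 0.944 | 0.954 |

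Most of the gain comes from keeping visits. Among all-visits fits the visit term changes power by -0.004, 0.001 and 0.010. At 5% loss and no shift, completers versus all visits with visit is 0.966 versus 0.973. With a top-dose effect of 1.54, power is 1.00 either way and only the SD gain remains. These simulations use within-participant least squares; the SE ratios above come from generalized least squares under compound symmetry and agree with them.

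**4. Aim 2, omitted visit.** Let d = effect + s x shift + e, with e of SD 1 and s = +1 or -1 by order. Without a visit term the error SD becomes about sqrt(1 + shift^2):
- shift 0.25: sqrt(1.0625) = 1.031, or 3%;
- shift 0.5: sqrt(1.25) = 1.118, or 12%.

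This is nearly the same under either kind of list. At n = 10 and shift 0.5, exact balance gives sqrt(1 + 0.25 x 10/9) = 1.130, against 1.118 under simple randomization. Power with balanced orders, without and then with the visit term, at paired effect 0.90:

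| Shift | n = 10 | n = 30 |
|---|---|---|
| 0 | 0.718, 0.705 | 0.998, 0.998 |
| 0.25 | 0.693, 0.703 | 0.997, 0.997 |
| 0.5 | 0.623, 0.704 | 0.994, 0.997 |

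At paired effect 1.54 and n = 30, power is 1.00 in every cell.

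**5. Chance imbalance under simple randomization.** A 21:9 or worse split of 30 has probability 0.043. It moves the unadjusted estimate by at least (21 - 9)/30 = 0.4 times the shift, which is 0.1 SD at a shift of 0.25.

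**6. Type I error without the visit term (Aim 2 model).** Simple randomization gives 0.049 to 0.051 at every shift. Balanced orders give 0.043 to 0.044 at shift 0.25 and 0.029 to 0.030 at shift 0.5. The test is never liberal.

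**The case against.** The strongest reply is that this is silence rather than error. The plan does not say how the AUC ANOVA is fitted, section 11.0 allows partial data, and the external statistician may already have built a balanced list. The documents give neither a dropout rate nor a visit difference. The washout, fasting, diet-log review, standard breakfast, matched chamber activity and identical procedures make a large visit difference less likely. Recruiting up to 30 against a stated need of 10 already covers attrition, and if the paired effect is about 1.54 there is no power left to gain. All of this stands, and it is why the point is optional.

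It does not remove the point. Section 12.0 uses a different name for the AUC analysis than for the dose x time analysis, so a classical fit is a natural reading, and the SD gain needs only some dropout.

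A reader might infer more than the documents support:
- **Bias or false positives.** Order is randomized, so the unadjusted comparison is unbiased over repeated randomization, and step 6 shows no excess type I error.
- **Unbalanced sequences as a fact.** The plan is silent on balance, which is not evidence of imbalance.
- **A threat to dose selection for Aim 2.** That choice is a ranking. In the simulations with 10% loss, the chance of ranking the best dose first rises only by about 0.01 to 0.03.
- **A visit term that is safe only with a balanced list.** Under simple randomization at shift 0.5 the term still helps: 0.621 to 0.656 in Aim 2 at n = 10, and 0.935 to 0.946 in Aim 1.

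**Conclusion.** The point holds as a conditional loss of precision. For the Aim 1 AUC with 30 enrolled, using all visits lowers the SD of the contrast by about 3% to 6% at an assumed 5% to 10% loss before each later visit. At 10% loss and a paired effect of 0.90, power rises from about 0.93 to 0.96. At about 1.54 there is no power gain. Without dropout or a visit difference there is no gain at all.

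In Aim 2 the benefit depends entirely on a real visit difference. If there is one, the error is inflated with or without balance, and lack of balance adds a chance movement of the estimate. With 30 participants the effect on Aim 2 power is negligible up to a shift of 0.5; it matters mainly if the final number is near 10.

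The loss rates, shifts and paired effects are assumptions. Severity: optional.

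**What to change.** 1. **Aim 1.** Analyse the AUC by a linear mixed model with condition and visit number as fixed effects and participant as random, on all available visits, keeping the Tukey comparisons. Add visit number to the dose x time model.
2. **Aim 2.** Replace the paired t-tests with the same condition-plus-visit model.
3. **Randomization list.** If it is not yet made or used, build it with sequences as balanced as the final n allows: a Williams square for Aim 1 and AB/BA blocks for Aim 2. Thirty is not a multiple of four, so Aim 1 would have 7 or 8 participants per sequence. If the list is already in use, state its form in section 6.0. Balance is preferable but not a precondition for the visit term.

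The cost is SAP wording, one model term and, if still possible, a balanced list; no extra visits. If there is no visit shift, the visit term costs a little power at paired effect 0.90. In Aim 2 at n = 10 it falls from 0.72 to 0.70 with balanced orders and from 0.72 to about 0.65 to 0.66 without; at n = 30 the cost is about 0.001 or less. In Aim 1 with 30 enrolled the cost is about 0.00 to 0.01 (0.959 to 0.955 with Williams orders, 0.960 to 0.949 with simple randomization). The all-visits model assumes that visits are missing at random, and the SAP should say so.

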3.0 Outcome Measures/Endpoints**3.1 Primary Outcome Measures****Specific Aim 1:**

Thermogenesis (i.e., resting energy expenditure) and thermogenesis area under the curve during the protocol. Thermogenesis will be measured using whole body indirect calorimetry, calculated using the Weir formula (5), will be measured every 30 minutes during the 6 hour protocols. Area under the curve for thermogenesis will be calculated to reflect the cumulative effect of mirabegron over time.

Specific Aim 2:

Core temperature deflection point during the progressive cold-water immersion challenge. Core temperature will be continuously measured using rectal thermistors. The point at which core temperature begins to fall (i.e., deflection point) will be identified using Prism 8 software by plotting core temperature vs. water temperature.

Specific Aim 3:

Gut microbiota phylotypes, fecal mirabegron concentration, and serum mirabegron concentration will be measured from samples obtained during the study (serum samples: pre-mirabegron/placebo and following 6 h of mild cold exposure; fecal samples: first bowel movement following 6 h of mild cold exposure). Samples will be assessed using bacterial DNA extraction and purification, polymerase chain reaction, and MinION analysis as well as metabolomics.

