Power Analysis: This aim is being conducted as an exploratory aim in conjunction with Specific Aim 1. As such, to be consistent, we expect to observe an effect size (δ) of 0.90 for the comparison of the gut microbiota in the placebo condition versus 200 mg of mirabegron. Given this effect size, 10 participants will be needed to achieve a power of 0.99 with an alpha level set at 0.05. To account for possible attrition, we plan on recruiting up to 30 participants.

Statistical Approach:

Principal Coordinate Analysis will be performed with group samples and any outliers will be identified. T-tests, and/or ANOVA will be performed to identify significant differences. Statistical analysis to detect variation between samples will be carried out using student t-test or Mann-Whitney test depending on data distribution. Multivariate statistics will be incorporated in a web-based tool Metastats, which can reveal, with high confidence, discriminatory functions between the replicated metagenome dataset of the gut microbiota of humans. In addition, the ShotgunFunctionalizeR and/or Primer E packages will be used for this analysis.

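### The Aim 2 power of 0.99 is stated for rectal temperature with an effect size carried over from Aim 1, and is not shown to apply to the primary test on the core temperature deflection point.

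*Combined protocol and SAP*

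**What the plan says.** Section 12.0, Aim 2 power analysis, expects an effect size of 0.90 "for the comparison of rectal temperature in the placebo condition versus the mirabegron condition". It introduces the value with "Similar to Specific Aim 1 and the data from" the cited acute-dosing study. It then states that 10 participants give power 0.99 at alpha 0.05, and that up to 30 will be recruited to cover attrition.

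The Aim 1 paragraph of the same section gives an effect size "of 0.90 for the comparison of resting energy expenditure in the placebo condition versus 200 mg of mirabegron", from the same study. The Aim 3 paragraph gives one "of 0.90 for the comparison of the gut microbiota in the placebo condition versus 200 mg of mirabegron", chosen for consistency with Aim 1.

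Section 3.1 names the Aim 2 primary outcome: "Core temperature deflection point during the progressive cold-water immersion challenge". It is the point where core temperature starts to fall, found in Prism 8 from a plot of core against water temperature. No unit is given for the value that enters the analysis. Section 12.0 compares it between conditions by paired t-test.

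On dose, Section 5.0 has Aim 2 participants take a placebo or "one dose of mirabegron (100 mg) prior to entering our water immersion tank", and Section 7.0 also writes 100 mg. Both sections add that the Aim 2 dose will be whichever gave the largest thermogenic response in Aim 1.

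**The concern.** A power statement describes a particular test on a particular variable. Here the variable in the power sentence (rectal temperature) is not, as worded, the variable in the primary test (a fitted breakpoint). A breakpoint has its own between-visit variability and its own fitting error, so a standardised effect on rectal temperature does not carry over to it. An effect on energy expenditure carries over even less.

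Nothing in the documents derives 0.90 for any Aim 2 outcome. The same value serves energy expenditure, rectal temperature and gut microbiota, which looks like carry-over and not three separate estimates.

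At stake is how the Aim 2 result will be read. With a stated power of 0.99, a null result could be taken as firm evidence that mirabegron does not delay the fall in core temperature, although the plan never says how large a delay it could detect. Correcting the arithmetic that leads from 0.90 to a sample size would not cure this.

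**Working it through.** **Inputs from the documents.** Effect size 0.90, n = 10, power 0.99, alpha 0.05 (sidedness not stated), up to 30 recruited, paired t-test (all Section 12.0). Cooling at 12°C per hour (Section 7.0). The documents do not give a difference or SD for the deflection point, the within-person correlation, or a dropout rate.

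**Formula.** For n pairs and standardised paired difference dz = mean difference / SD of differences, the test statistic is noncentral t with n − 1 degrees of freedom and noncentrality dz·√n. Power is the probability that its absolute value exceeds the two-sided 5% critical value.

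**Step 1: the plan's own figure.** With dz = 0.90 and n = 10, noncentrality is 0.90 × √10 = 2.85.
- Power is 0.72 two-sided or 0.84 one-sided, so 0.99 is not reproduced.
- Power 0.99 at dz = 0.90 needs 25 pairs two-sided or 21 one-sided.
- With 10 pairs, power 0.99 two-sided needs dz = 1.53. If 0.90 is in raw-SD units, dz = 0.90/√(2(1 − r)), so r = 1 − (0.90/1.53)²/2 ≈ 0.83. No such correlation is stated.

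**Step 2: what 0.90 is attached to.**

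| Aim | Outcome named with 0.90 | Dose named with it | Primary outcome in Section 3.1 |
|---|---|---|---|
| 1 | Resting energy expenditure | 200 mg | Resting energy expenditure and its AUC |
| 2 | Rectal temperature | None | Core temperature deflection point |
| 3 | Gut microbiota | 200 mg | Microbiota phylotypes; fecal and serum mirabegron |

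The results that the protocol reports from the cited study are energy expenditure and supraclavicular skin temperature (Section 1.0), and heart rate and blood pressure (Section 9.0). It reports no rectal temperature or deflection result.

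**Step 3: power of the primary test if dz is unknown** (two-sided 0.05; dz values are assumptions).

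| dz | Power, 10 pairs | Power, 30 pairs |
|---|---|---|
| 0.3 | 0.14 | 0.36 |
| 0.5 | 0.29 | 0.75 |
| 0.7 | 0.51 | 0.96 |
| 0.9 | 0.72 | 0.997 |

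**Step 4: detectable difference.** Solving for dz at 80% power gives 0.996 with 10 pairs and 0.529 with 30 pairs, that is 1.00 and 0.53 SD of the paired difference. At 90% power the values are 1.15 and 0.61 SD.

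**Step 5: conversion, only if the unit is water temperature.** At 12°C per hour, 1°C corresponds to 60/12 = 5 minutes. The SD of the paired difference is an assumption throughout. Each entry is SD × 0.996 or SD × 0.529, then × 5 for minutes.

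| Assumed SD | 10 pairs, 80% power | 30 pairs, 80% power |
|---|---|---|
| 1°C | 1.0°C (5 min) | 0.5°C (about 3 min) |
| 3°C | 3.0°C (15 min) | 1.6°C (about 8 min) |
| 6°C | 6.0°C (30 min) | 3.2°C (about 16 min) |

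**The case against.** **Rectal temperature may be shorthand.** The deflection point is derived from rectal thermistor data, so the power sentence may simply name the endpoint loosely. A reader might also infer that the endpoint is definitely a water temperature. The documents do not say so: Section 3.1 gives no unit, and Section 3.2 reads the parallel shivering endpoint as a core temperature. Water temperature is the natural reading, because it is the other axis of the plot and the objective in Section 2.1 is a delay, but it remains an inference. What stands is that no unit is given, and on either reading no difference or SD for the breakpoint is given.

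**The dose is not fixed.** A reader might infer a settled mismatch of 100 mg against 200 mg and scale 0.90 down in proportion. The text does not support that. The Aim 2 power sentence names no dose, and Sections 5.0 and 7.0 also tie the dose to the Aim 1 result. Under that rule 100 mg would be used only if its Aim 1 response were the largest, which does not fit with halving its effect. The only dose-response that the protocol states is for heart rate and blood pressure (Section 9.0). What stands is that the two dose statements disagree.

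**The cited study may contain temperature data.** The documents cannot exclude this. The supportable statement is that the protocol shows no derivation, and that 0.90 is linked explicitly to energy expenditure alone in Aim 1.

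**Up to 30 may be enough.** If all 30 complete, power is 0.997 at dz = 0.90 and at least 0.80 for dz of about 0.53 or more. This is a fair point, and it limits the consequence. It does not make 0.99 with 10 participants a property of the primary test.

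**Conclusion.** The concern holds as a wrongly based power statement. The 0.99 for Aim 2 is attached to rectal temperature, rests on a value that the documents tie to another outcome in Aim 1, and is not shown to apply to the paired t-test on the deflection point. What can be said of that test is that 80% power requires a true difference of 1.00 SD with 10 pairs or 0.53 SD with 30.

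These figures assume two-sided alpha 0.05, approximately normal paired differences, and 10 or 30 complete pairs. Any value in °C or minutes depends further on an assumed SD and on water temperature being the unit.

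A reader might conclude that Aim 2 is too small. The documents do not establish that, because they give no expected difference or SD, and recruitment may reach 30. The matter is of moderate weight and should be corrected before the Aim 2 result is interpreted.

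**What to change.** Withdraw the 0.99 claim and the 0.90 effect size from the Aim 2 paragraph of Section 12.0, and put a detectable-difference statement in their place. For example:

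> The primary comparison is a two-sided paired t-test (alpha 0.05) on the deflection point, analysed in [unit]. With 80% power it detects a mean difference of 1.00 SD of the paired difference with 10 complete pairs and 0.53 SD with 30. For an assumed SD of [range], this is [range in that unit].

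Alongside this:
- State in Section 3.1 the unit in which the deflection point is analysed. If it is water temperature, also give the detectable difference in minutes (1°C = 5 minutes).
- Label the SD range as an assumption, and state the number of complete pairs expected.
- Report the Aim 2 result as a mean paired difference with its confidence interval, so that a null result shows which delays remain compatible with the data.
- Reconcile the 100 mg entries in Sections 5.0 and 7.0 with the rule in the same sections that the dose depends on Aim 1.

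The cost is one rewritten paragraph, the short clarifications above and a less favourable stated power. Enrolment does not change.
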